**Footnotes:**

- a. Informed consent to be obtained before any other study procedures are performed.
- b. Medical history, including previous cancer therapies, cancer history, and past and ongoing concomitant illnesses which are relevant to the disease under study.
- c. A complete physical examination is required at screening and end of study/early termination. Directed physical examinations may be limited to problem focused review of symptoms and major organ systems. This should include an assessment for signs and symptoms of peripheral neuropathy as this is a known adverse event associated with MMAE-based ADCs and may be expected to occur with OBI-999.
- d. Height to be obtained at screening only.
- e. Vital signs include temperature, blood pressure and pulse. Temperature measurement will be obtained as clinically indicated.
- f. Performed by ophthalmologist as follows:
  - Part A - At screening, every 2 cycles for the first 6 months (C2, C4, C6, C8), then every 3 cycles thereafter (C11, C14 and so on), and the end of study/early termination visit.
  - Part B – At screening and at the discretion of the Investigator during the course of the study.
- g. ECOG performance status: at screening, D1 of each cycle, and end of study/early termination
- h. 12-lead ECG with assessment of QTcF: at screening, Cycle 1 Day 1, Cycle 1 Day 3 ( $48\pm 2$  hours after the end of the Cycle 1 Day 1 OBI-999 infusion) and EoS/ET. The ECG testing on C1D4 could be tested 24 hours before but no later than C1D4.
- i. Pregnancy testing should be performed in females of childbearing potential only. A serum pregnancy test is required during screening. A urine or serum pregnancy test is acceptable end of study or early termination
- j. Tumor biopsy samples are mandatory at screening visit. Fresh (preferred) tissue or archival tissue is acceptable. A minimum of 5 slides are required for the central laboratory Globo H assay for determination of eligibility in Part B. Up to 10 unstained additional slides should be provided, depending on availability, for the protocol defined exploratory studies.
- k. Hematology and Serum chemistry (Laboratory Assessments: [Table 12-1](#)). Blood draw is prior to OBI-999 infusion. For C2D1 and each cycle after, laboratory assessments may be drawn 72 hours in an advance of infusion.  
Hematology: hematocrit, hemoglobin, erythrocyte count, white blood count, absolute counts of leukocytes, neutrophils, lymphocytes, monocytes, eosinophils, basophils, and platelet count.  
Serum chemistry: sodium, potassium, chloride, bicarbonate, blood urea nitrogen, creatinine, glucose, calcium, phosphorus, magnesium, total protein, albumin, alanine aminotransferase, aspartate aminotransferase, alkaline phosphatase, creatine kinase, lactate dehydrogenase, total bilirubin, and uric acid. Creatinine clearance will be calculated by Cockcroft Gault equation at screen visit, week 1 and EoS/ET.

I. Coagulation, and Urinalysis (Laboratory Assessments: [Table 12-1](#)). Blood draw and urine collection is prior to OBI-999 infusion. Only urinalysis will be collected at Day 1 of Cycles 2-35.

Coagulation: prothrombin time, activated partial thromboplastin time, and international normalized ratio.

Urinalysis: specific gravity, pH, protein, glucose, ketones, bilirubin, urobilinogen, blood, nitrite, leukocyte esterase as assessed by dipstick. A microscopic urinalysis (only if needed) evaluating white blood cells, red blood cells, epithelial cells, bacteria, cast and crystals

m. OBI-999 is given on Day 1 of each 21-day cycle until DLT, disease progression, unacceptable toxicity, or withdrawal of consent, whichever occurs earlier.

n. Pharmacokinetic: (for analysis of serum concentration of OBI-999 total antibody, ADC and free MMAE). Detailed sampling schedule in [Table 9-2](#) (Part A) and [Table 9-3](#) (Part B).

o. Immunogenicity studies (ADA) - ADA samples will be collected. Detailed sampling schedule in [Table 9-2](#) (Part A) and [Table 9-3](#) (Part B). For patients with persistent antibodies at end of study, an additional ADA sample will be collected at 4 months after the end of study visit.

p. Radiology (CT or MRI scan) evaluations of tumor response: Performed during screening and during the study every 6 weeks for the first 3 months, and then every 9 weeks until discontinuation of study treatment, disease progression, death, or initiation of further systemic cancer therapy, including radiation therapy, whichever occurs earlier. CT or MRI scan will be performed within 1 week prior to the start of the next cycle. Unscheduled scan can be performed anytime, if needed to confirm disease progression. Radiology assessment for early termination/end of study, should ONLY be performed if  $\geq 9$  weeks have passed from the previous scheduled CT/MRI scan. Same assessment method and same technique should be used on each patient while on study.

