# 7 Selection and Withdrawal of Patients

## 7.1 Inclusion and Exclusion Criteria

### 7.1.1 Inclusion Criteria

Patients must meet all of the following criteria in order to be included in the study (for both Parts A and B unless specified otherwise):

1. Male or female patients, 18 years of age or older at the time of consent.
2. Provide written informed consent prior to performing any study-related procedure.
3. Histologically or cytologically confirmed patients with advanced solid tumors.

4. Patients must have been treated with established standard-of-care therapy, or physicians have determined that such established therapy is not sufficiently efficacious, or patients have declined to receive standard-of-care therapy. In the latter case, the informed consent must state the effective therapies the patient is declining.
5. Measurable disease (i.e., at least one measurable lesion per RECIST 1.1) ([Eisenhauer, et al., 2009](#)).
6. Eastern Cooperative Oncology Group (ECOG) performance status of 0 or 1 ([Oken, et al., 1982](#)).
7. Adequate organ function defined as:
  - a. Hepatic:
    - i. Serum ALT  $\leq 3 \times$  upper limit of normal (ULN),  $\leq 5 \times$  ULN in the presence of liver metastases
    - ii. Serum AST  $\leq 3 \times$  ULN,  $\leq 5 \times$  ULN in presence of liver metastases
    - iii. Serum bilirubin  $\leq 1.5 \times$  ULN (unless due to Gilbert's syndrome or hemolysis)
  - b. Renal:
    - i. Creatinine clearance  $> 50$  mL/minute using Cockcroft Gault equation
  - c. Hematologic:
    - i. Absolute neutrophil count  $\geq 1,500/\mu\text{L}$
    - ii. Platelets  $\geq 100,000/\mu\text{L}$
    - iii. Hemoglobin  $\geq 8 \text{ g/dL}$
8. Patient is willing and able to comply with all protocol-required assessments, visits, and procedures, including a pretreatment tumor biopsy. Archival tumor biopsies are acceptable at baseline.
9. Females of childbearing potential must have negative serum pregnancy test prior to starting study therapy, and agree to use a reliable form of contraceptive during the study treatment period and for at least 120 days following the last dose of study drug.  
Patient not of childbearing potential (i.e., permanently sterilized, postmenopausal) can be included in study. Postmenopausal is defined as 12 months with no menses without an alternative medical cause.  

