**Table 9-1 Schedule of Assessments**

Study Procedure	Screening Visit	Treatment Period						EoS / ET	F/U
		Cycle 1					Cycle 2-35		
Cycle (C) #	-								
Cycle # and Day		C1D1	C1D2	C1D4	C1D8	C1D11	C1D15	D1	
Window period (days)	-28 to -1	-1*	±1	±3	±3	±3	±3	±3	±7
Informed consent a	X								
Demographics	X								
Eligibility screening	X	X							
Medical history b	X	X							
Physical examination c	X	X			X*		X	X	X
Height, weight d	X d	X					X	X	
Vital signs e	X	X					X	X	
Ophthalmology examination f	X						Q6wk for the first 6 months, then Q9wk thereafter f		X
ECOG g	X						X	X	
12-lead ECG h	X	X		X g				X	
Pregnancy testing i	X							X	
Tumor biopsy j	X								
Hematology and serum chemistry k	X	X			X		X	Every week for Cycles 2 and 3, then D1 of Cycles 4+	X
Coagulation and urinalysis l	X							D1 of each 21-day cycle l	X
Drug administration m		X						D1 of each 21-day cycle	
Pharmacokinetic sample n			See footnote n						
Immunogenicity (ADA) o		X						See footnote o	X
Radiology evaluations (CT or MRI) p	X							Q6wk for the first 3 months, then Q9wk thereafter	X
Concomitant medications		↔							
Adverse events		↔							→

Abbreviations: ADA = anti-drug antibody; D = Day; C = Cycle; CT = computed tomography; ECG = electrocardiogram; ECOG = Eastern Cooperative Oncology Group; EoS = End of Study; ET = Early Termination; F/U = follow-up; MRI = magnetic resonance imaging; Q6wk = every 6 weeks; Q9wk = every 9 weeks

EoS Visit is the safety follow-up visit, conducted  $28\pm 7$  days after the last OBI-999 dose. ET Visit lab assessments will be conducted for patients discontinuing study treatment, if last available tests are before 2 weeks.

\*The - 1 day window (1 day prior) for C1D1 is for safety laboratory assessments. Blood can be drawn 1 day prior to initiation of study drug infusion on C1D1. Safety laboratory results should be available and reviewed by the Investigator prior to the OBI-999 administration.

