**Table 12-1      Laboratory Assessments**

Hematology	Serum chemistry	Urine analysis (dipstick)

 
• Hemoglobin (Hb)
 
• Hematocrit
 
• Mean corpuscular hemoglobin (MCH)
 
• Mean corpuscular hemoglobin concentration (MCHC)
 
• Mean corpuscular volume (MCV)
 
• Platelet count
 
• Red blood cell (RBC) count
 
• White blood cell (WBC) count with differential
 
	
 
• Albumin
 
• Alanine aminotransferase (ALT)
 
• Alkaline phosphatase (ALP)
 
• Aspartate aminotransferase (AST)
 
• Blood urea nitrogen (BUN) or Urea
 
• Bicarbonate
 
• Creatinine
 
• Creatine kinase
 
• Electrolytes (Na, K, Cl, Ca, P, Mg)
 
• Glucose
 
• Lactate dehydrogenase (LDH)
 
• Total bilirubin
 
• Total protein
 
• Uric acid
 
	
 
• Appearance
 
• Blood
 
• pH
 
• Protein
 
• Glucose
 
• Ketones
 
• Nitrite
 
• Leukocyte esterase
 
• Specific gravity
 
• Urine human chorionic gonadotropin (HCG) (pre-menopausal females only)
 
• Urobilinogen
 
• Bilirubin
 
• Microscopic, as needed
 

Coagulation	Pregnancy test	

 
• Prothrombin time (PT)
 
• International Normalized Ratio (INR)
 
• Activated partial thromboplastin time (aPTT)
 
	To be performed on all female patients of child-bearing potential at the screening visit and early termination visit.	

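### The only pregnancy test required before dose 1 may be up to 28 days old, and on the dominant reading none is scheduled before doses 2 to 35

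*Protocol*

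**What the plan says.** **Before dose 1.** Inclusion criterion 9 (Protocol Section 7.1.1) states: "Females of childbearing potential must have negative serum pregnancy test prior to starting study therapy". It gives no maximum interval. Table 9-1 marks pregnancy testing at screening (Day -28 to -1) and at EoS/ET, and footnote i matches: "A serum pregnancy test is required during screening. A urine or serum pregnancy test is acceptable end of study or early termination". The Cycle 1 Day 1 column is marked for eligibility, medical history and safety bloods, and the note under the table adds: "Safety laboratory results should be available and reviewed by the Investigator prior to the OBI-999 administration". Neither the pregnancy row nor the urinalysis row is marked in that column.

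**During treatment.** Section 12.5.4 asks for a negative test at screening and at EoS/ET. The pregnancy cell of Table 12-1 says: "To be performed on all female patients of child-bearing potential at the screening visit and early termination visit". The urinalysis column of the same table, however, lists "Urine human chorionic gonadotropin (HCG) (pre-menopausal females only". Footnote l of Table 9-1 cites Table 12-1 and states "Blood draw and urine collection is prior to OBI-999 infusion" and "Only urinalysis will be collected at Day 1 of Cycles 2-35". Its own analyte list is: "Urinalysis: specific gravity, pH, protein, glucose, ketones, bilirubin, urobilinogen, blood, nitrite, leukocyte esterase as assessed by dipstick".

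**If a test is positive.** Section 12.5.4 requires reporting and follow-up of a known pregnancy and does not mention dosing. Footnote m's list of reasons to stop omits pregnancy. Section 7.2 has an open list of reasons for which a patient may be withdrawn, including a change that makes her ineligible under the entry criteria.

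SAP Appendix I copies the Table 9-1 schedule and footnote i.

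**The concern.** OBI-999 carries MMAE, which Section 4.2 describes as a highly potent antimitotic agent. The protocol requires contraception until at least 120 days after the last dose, so it already treats reproductive exposure as a risk. Contraception lowers the chance of conception but does not detect it.

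A woman tested early in screening may be too early in a pregnancy for the test to show it, or may conceive before Cycle 1 Day 1. She can then be dosed in full compliance with the protocol. If no test is done before later infusions, exposure can continue until symptoms, an unscheduled test or the end-of-treatment visits reveal the pregnancy. Sites that interpret the stray hCG line differently would also monitor similar patients differently.

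**Working it through.** No sample-size or error-rate figure is involved. The check is a comparison of provisions followed by a day count.

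**Step 1: which provisions set the timing of pregnancy tests?**

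| Provision | Screening | C1D1 | Day 1, Cycles 2-35 | EoS/ET |
|---|---|---|---|---|
| Table 9-1, pregnancy row | yes | no | no | yes |
| Footnote i | yes (serum) | no | no | yes (urine or serum) |
| Section 12.5.4 | yes (serum) | no | no | yes (serum or urine) |
| Table 12-1, pregnancy cell | yes | no | no | ET only |
| Table 12-1 urine panel via footnote l | if hCG counts as urinalysis | no | if hCG counts as urinalysis | if hCG counts as urinalysis |

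The columns of Table 9-1 are partly broken in the text available. Footnote i, Section 12.5.4 and the pregnancy cell confirm the timing without it.

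The first four rows agree that no test is scheduled at C1D1 or between doses. This is the dominant reading. The last row is the only source of doubt. Footnote l's analyte list omits hCG, which favours the dominant reading. It also omits appearance, another item in the Table 12-1 column, so the list is not an exact copy of the panel and does not settle the matter. The populations differ too: pre-menopausal women in the urine panel, women of child-bearing potential in footnote i. On neither reading is there a test at C1D1.

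**Step 2: age of the last scheduled test at each dose, dominant reading.**

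Inputs: screening test s = 1 to 28 days before dose 1 (Table 9-1); 21-day cycles, at most 35 (Section 8.2.2). With doses on schedule, the age at dose k is s + 21 × (k - 1).

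- Dose 1: 1 to 28 days.
- Dose 2: 1 + 21 = 22 to 28 + 21 = 49 days.
- Dose 35 (theoretical maximum, for a patient given every dose): 21 × 34 = 714, hence 715 to 742 days.

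**Step 3: first dedicated test after dose 1.**

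The EoS visit is 28 ± 7 days after the last dose, which is 21 to 35 days. A patient who stops early may be tested sooner, at an early termination visit (Section 7.3, footnote i).

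**Step 4: the same quantity under the proposed schedule.**

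Dose 1: 0 to 1 day. Later doses: 0 to 3 days, using the 72-hour allowance that footnote k already gives for bloods.

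**The case against.** A reader might infer that the protocol contradicts itself on testing before doses 2 to 35. The documents do not support that. Four provisions agree, Section 12.4 leaves visit timing to Table 9-1, and the urine hCG line has an ordinary explanation: a urine test is allowed at EoS/ET. It may be a misplaced entry. What stands is that the line creates ambiguity; if it is disregarded, the on-treatment gap remains.

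A reader might also infer that untested intervals of about two years are typical. They are not shown to be. Such an interval requires all 35 doses, and treatment ends at progression. Among 13 Part A patients with a response assessment, the best response was stable disease, in 5 (Section 4.4). The figures that carry the point are those for doses 1 and 2.

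Nor is it right that nothing in the text would let a site stop dosing. Section 7.2 is open-ended, includes loss of eligibility and Investigator judgment, and Section 12.2 has examinations that verify continued eligibility. Unscheduled assessments are also allowed (Section 9.2). This wording is permissive, however. Criterion 9 is tied to the start of therapy, and the exclusion list does not name pregnancy, so an explicit instruction is missing.

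Finally, the sponsor stopped the study on 10 November 2023 (SAP Section 3). The practical benefit is therefore limited to any patient still dosed under this version and to any protocol that reuses the schedule.

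**Conclusion.** The concern holds in this form. A serum result 1 to 28 days old is enough for dose 1 on any reading of the protocol. On the dominant reading no pregnancy test is scheduled before doses 2 to 35, and the last one is 22 to 49 days old at dose 2. The hCG line in the urine panel makes this unclear rather than contradictory. Pregnancy is covered as a reason to stop only by general wording.

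The day counts assume doses on schedule. The documents do not give the share of women of child-bearing potential or a typical treatment duration, so no number of affected patients can be stated. This is a patient-safety gap that should be closed; it does not affect any statistical analysis.

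**What to change.** - **Table 9-1:** mark the pregnancy row at C1D1 and at Day 1 of Cycles 2-35.
- **Footnote i:** replace with: *Women of child-bearing potential: serum test at screening; urine or serum hCG before infusion on Day 1 of every cycle (Cycle 1: on Day 1 or the day before; from Cycle 2: within 72 hours before infusion); urine or serum at EoS/ET. The result must be known before infusion. If positive, withhold OBI-999 and test serum; resume only if serum is negative or the Investigator has otherwise excluded pregnancy; if pregnancy is confirmed, discontinue OBI-999 permanently.*
- **Table 12-1:** move the hCG line from the urine panel to the pregnancy cell with this timing, add end of study, and use child-bearing potential as the population.
- **Section 12.5.4:** state the same schedule and the instruction to stop.
- **Section 7.2 and footnote m:** add confirmed pregnancy.

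**Cost.** No added visit. On the dominant reading the change adds one low-cost hCG test per dose, at most 35 per woman. Blood is already drawn at C1D1, where a urine test would need one extra sample. From Cycle 2 urine is already collected before infusion. There will be occasional false positives. If confirmation takes longer than the ±3-day dosing window, that dose is skipped (Section 8.3). The route for a serum-positive woman in whom pregnancy has been excluded matters because interruption for more than two consecutive doses may end treatment.

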### **6.1.1 Part A – Dose-Escalation**

Up to 30 eligible patients with advanced solid tumors will be enrolled in Part A. No Globo H expression testing will be required for inclusion.

Five cohorts of escalating dose levels of 0.4, 0.8, 1.2, 1.6, and 2.0 mg/kg (capping calculations at a maximum of 100 kg) OBI-999 were planned to be enrolled and assessed using a 3+3 design to identify the MTD and RP2D. The RP2D of OBI-999 was determined to be 1.2 mg/kg (capping administered dose to a maximum of 120 mg for 100 kg) administered on Day 1 of each 21-day cycle.

Three patients were enrolled at the lowest dose level. If none of the 3 patients experienced a DLT in the first 21-day cycle, the next cohort of 3 patients was enrolled at the next higher dose level. If 1 of 3 patients in the initial dose cohort experienced a DLT, that cohort was expanded to 6 patients. If only 1 of these 6 patients had a DLT, the next cohort of 3 patients was enrolled at the next higher dose level. If 2 or more patients of the 3-6 patients in a cohort experienced a DLT, dose-escalation ceased, and the lower dose level was designated the MTD, where no more than 1 of 6 patients experienced at DLT. New patients were enrolled at the previous lower (tolerated) dose level until that cohort had 6 patients. This lower dose level was considered the MTD if  $\leq 1$  in 6 patients had a DLT.

A patient who withdraws from the study within the DLT evaluation period for reasons other than drug-related AE will be replaced.

Escalation to higher OBI-999 dose cohorts is not permitted during the study. After a DLT is experienced by a patient, dose interruption, modifications, or dose delays may apply, as per Investigator judgement (refer protocol [Section 8.3](#)).

Patients will continue to receive treatment with OBI-999 until disease progression, unacceptable toxicity, consent withdrawal, or for up to 35 cycles (approximately 2 years), whichever occurs first.

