## 6.2 Definition of Dose-Limiting Toxicities (Part A only)

A DLT is defined as the occurrence of any of the following events, within the first cycle of treatment that is considered to be at least possibly related to OBI-999:

- Grade 4 neutropenia lasting more than 7 days.
- Febrile neutropenia.
- Grade 4 thrombocytopenia.
- Grade 3 thrombocytopenia with  $\geq$  Grade 2 bleeding requiring platelet transfusions.
- Grade 3 fatigue, nausea and vomiting or diarrhea that does not resolve to Grade 1 or Baseline within 72 hours despite optimal supportive care.
- Any Grade 4 gastrointestinal (GI) toxicity.
- Any other Grade 3 or Grade 4 non-hematological toxicity (except Grade 3 fatigue, nausea, vomiting, or diarrhea lasting  $<24$  hours with optimal therapy, Grade 3 non-hematologic laboratory abnormalities that resolve to Grade 1 or Baseline within 14 days).

All AEs unless they are determined to be not related to study drug will be taken into consideration in determining DLTs. NCI CTCAE version 5.0 will be the basis for the descriptive terminology and grading of AEs. The period for DLT observation is 21 days from the start of first dose of OBI-999 (i.e., Day 1).

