## **8.3 Dose Modifications and Toxicity Management**

Escalation to a higher OBI-999 dose cohort is not permitted during the study.

Dose modifications for hematologic toxicity, non-hematologic toxicity, and infusion reactions should be independently assessed at each visit. Recommendations for dose modifications for toxicity are provided in Table 8-1.

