**Table 8-1 OBI-999 Dose Modifications for Toxicity**

Toxicity	Hold Dose	% of Full Dose after Recovery to Grade 0-1
Grade 1	Do not hold dose	100
Grade 2	Hold dose until resolution to Grade 0 or 1	75
Grade 3	Hold dose until resolution to Grade 0 or 1	75
Grade 4	Treatment should be discontinued	Not applicable

Once the dose has been reduced for toxicity and found to be well tolerated, re-escalation may be permitted at the Investigator's discretion. If a patient requires dose reductions on more than 2 occasions for toxicity related to OBI-999, the patient should discontinue from the study.

All reasons for treatment modifications should be fully explained.

The study drug dose which is not administered within the permitted window period of  $\pm 3$  days, must be skipped, and the next dose will be administered as per protocol schedule. Any skipped dose due to safety reason and if medically justified, for OBI-999 treatment related or unrelated reasons, will not be captured as a protocol deviation for this study.

Treatment interruption for more than 2 consecutive doses for related or unrelated reasons may necessitate discontinuation of study treatment.

Treatment interruption for intercurrent non-treatment related AEs will be at the Investigator's discretion and based on the well-being of the patient. All reasons for treatment interruption and

delays should be fully explained. Treatment for hematologic and non-hematologic toxicity may be implemented as clinically indicated according to institutional guidelines. Refer Table 8-2 for therapeutic antiemetic and anti-diarrheal recommendations.

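### The schedule footnote ends OBI-999 at a DLT, while Section 6.1.1 and the Section 8.3 toxicity rules allow dosing to continue after one; in Part B the footnote's DLT trigger has no defined event

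*Protocol*

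**What the plan says.** Footnote m to the schedule of assessments (Protocol Table 9-1; same footnote in SAP Appendix I) reads "OBI-999 is given on Day 1 of each 21-day cycle until DLT, disease progression, unacceptable toxicity, or withdrawal of consent, whichever occurs earlier".

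Protocol Section 6.1.1 reads "After a DLT is experienced by a patient, dose interruption, modifications, or dose delays may apply, as per Investigator judgement" and refers the reader to Section 8.3. The synopsis has the same sentence without the reference, and SAP Section 5.1.1 has it with the reference. Section 6.1.1 then gives its own list of events that end treatment: "Patients will continue to receive treatment with OBI-999 until disease progression, unacceptable toxicity, consent withdrawal, or for up to 35 cycles". A DLT is not on it.

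Section 8.3 opens with "Recommendations for dose modifications for toxicity are provided in Table 8-1". In that table the Grade 2 and Grade 3 rows say "Hold dose until resolution to Grade 0 or 1", followed by 75% of the full dose. The Grade 4 row says "Treatment should be discontinued", with no condition on relatedness, type of toxicity, duration or DLT status. Section 8.3.1.1 permits retreatment after a Grade 3 infusion reaction. Section 8.3.2.1 permits restart at a reduced dose after Grade 3 neuropathy.

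The DLT definition in Section 6.2 covers Part A and the first 21 days. It includes "Any other Grade 3 or Grade 4 non-hematological toxicity", with stated exceptions. Section 7.2 lists Grade 4 infusion reactions and related toxicity among the reasons for which a patient may be withdrawn from treatment.

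**The concern.** The schedule table is a natural reference for site staff, and its footnote gives a DLT a different consequence from the body of the protocol. Two Part A patients with the same Cycle 1 event could be handled differently, each in accordance with a passage of the protocol. That is a patient-safety and consistency matter first.

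It also touches two outputs that SAP version 2.0 keeps for the abbreviated report: the tables of TEAEs leading to discontinuation of OBI-999 (starred in SAP Section 10.7.1) and the summary of extent of exposure (retained in SAP Section 11). Both depend on the stopping rule that sites followed. A reader of the report could not tell whether a discontinuation after a DLT reflects the event or the page that was consulted.

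**Working it through.** The documents state no figure on this point, so the check is to apply each passage to four kinds of event.

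| Event | Footnote m | Synopsis, Section 6.1.1, SAP 5.1.1 | Sections 8.3 and 7.2 |
|---|---|---|---|
| 1. Grade 3 DLT, Part A Cycle 1 | Stop | Interruption, modification or delay may apply; DLT not a stop event | Table 8-1: hold, then resume at 75%. 8.3.1.1 (infusion reaction) and 8.3.2.1 (neuropathy) also allow further dosing |
| 2. Grade 4 DLT, e.g. Grade 4 thrombocytopenia | Stop | Investigator judgement; the two numbered sections point to 8.3 | Table 8-1: should be discontinued. 7.2: may be withdrawn |
| 3. Grade 4 event in Part A Cycle 1 that is not a DLT | DLT trigger not met; stops only if judged unacceptable toxicity | Post-DLT sentence does not apply; stops only if judged unacceptable toxicity | Table 8-1: should be discontinued. 7.2, if related: may be withdrawn |
| 4. Grade 4 event after Cycle 1 or in Part B | Cannot be a DLT; otherwise as row 3 | As row 3 | As row 3 |

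**Row 1 is a direct contradiction.** A related Grade 3 neuropathy or infusion reaction in Cycle 1 is non-hematological and is not among the Section 6.2 exceptions, so it can be a DLT. Footnote m then ends treatment, while the other passages allow it to continue.

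**Row 2 is inconsistent in wording.** Footnote m and Table 8-1 agree, Section 6.1.1 leaves the matter to judgement, and Section 7.2 uses a permissive verb.

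**Rows 3 and 4 are not contradictions in logic.** Footnote m and Section 6.1.1 both end treatment for unacceptable toxicity, a term the documents do not define, and Table 8-1 is compatible with that. What remains is the gap between should in Table 8-1 and may in Section 7.2.

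**Part B.** Table 9-1 serves both parts, but Section 6.2 is limited to Part A. The DLT trigger therefore has no defined event in Part B.

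**Does a precedence rule settle it?** Protocol Section 14 says the SAP supersedes the protocol where they differ. The SAP carries both rules (Section 5.1.1 and Appendix I), so this does not resolve the conflict.

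**Effect on exposure.** The DLT period is 21 days from the first dose, and the second dose is nominally due on Day 1 + 21 = Day 22. A patient stopped under footnote m would normally have had one infusion. SAP Section 10.8.1 defines extent of exposure as last dose date − first dose date + 1, which gives 1 day. Under the other passages the value is not fixed, because dosing may resume.

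**The case against.** The strongest reply is that this matters little now. DLTs exist only in Part A and only in the first 21 days, Part A was complete when the SAP was written, and the sponsor stopped the study on 10 November 2023. Whether footnote m read the same way while DLTs were being managed cannot be seen from the current documents. This stands and limits the point to document correction and reporting.

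A second reply is that Section 6.1.1 points to Section 8.3 in the same sentence, so general discretion gives way to the specific table. That largely settles the Grade 4 DLT case within the body of the protocol. It does not help with a Grade 3 DLT, where Section 8.3 itself allows dosing to resume and footnote m does not.

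Third, Table 8-1 is introduced as recommendations and says should, so it is not an absolute stop. This also stands.

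A reader might infer four stronger things that the documents do not support:

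- **Every non-DLT Grade 4 event has two opposed outcomes.** The usual example is Grade 4 neutropenia of 7 days or less, since the Section 6.2 item is "Grade 4 neutropenia lasting more than 7 days". The DLT definition serves dose-finding and Table 8-1 serves the individual patient's dosing. No passage says such a patient must continue.
- **A dose level could look tolerable while all its patients were taken off drug.** This is an arithmetic extreme. Under Section 14.6 the RP2D rested on cumulative toxicities as well as DLT counts.
- **Footnote m removes the 35-cycle limit.** The table it annotates has a column for Cycles 2-35.
- **Part B responders lose their confirming scan through this conflict.** No DLT is defined in Part B. That argument rests on the scan-stopping rule in footnote p, and Section 10 calls for an end-of-treatment scan unless progression is already confirmed.

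**Conclusion.** The contradiction between footnote m and the synopsis, Section 6.1.1 and SAP Section 5.1.1 is real, appears in both documents, and is not settled by any precedence rule. It is sharpest for Grade 3 DLTs, where Section 8.3 also allows dosing to resume. The wording on Grade 4 toxicity in Table 8-1, Section 7.2 and Section 6.1.1 is a lesser inconsistency.

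Its reach is limited. The direct conflict can affect only those of the 22 Part A patients who had a DLT, and the documents do not say how many there were. In Part B the fault is an undefined trigger. What is exposed is the consistency of treatment stopping, and with it the interpretation of the discontinuation tables and extent of exposure. The objective response analysis and the two-stage design are not undermined.

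This conclusion assumes that a DLT is not automatically unacceptable toxicity. Section 6.1.1 implies as much by allowing dose modification after a DLT. If the sponsor intended the two to be equivalent, Section 6.1.1 is the passage out of line, and the need to reconcile is the same.

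**What to change.** The sponsor and Safety Review Committee should reconcile the synopsis, Sections 6.1.1, 7.2, 8.3.1.1 and 8.3.2.1, Table 8-1 and Table 9-1 footnote m of the protocol with SAP Section 5.1.1 and the Appendix I footnote, so that each event has one stated consequence in each part. Which consequence applies is their clinical decision, and none is proposed here. Whether the footnote's DLT trigger has any role in Part B should be stated explicitly.

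Since the study has stopped, the abbreviated report should carry a short note beside the table of TEAEs leading to discontinuation of OBI-999, saying that the documents gave differing instructions after a DLT. It can draw on what is already recorded: the action taken with study drug and the reason for treatment discontinuation, which Protocol Sections 12.5.1 and 7.3 require on the eCRF. Nothing shows that the rule a site applied was collected, so no such variable should be assumed.

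The cost is wording in a footnote and its cross-references, plus one table note. No new data or analysis is needed.
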